4.4.5 UNSCHEDULED VISITS

An unscheduled visit is defined as an interim visit requested by the participant or investigator due to an unanticipated problem. Data recorded at these visits will be entered into the database. Only relevant and applicable unscheduled visit information will be included in the final report as deemed necessary by the lead investigator.

4.5 STUDY PROCEDURES

The study procedures are summarized in Table 5.

Table 5: Summary of procedures to be conducted at scheduled visits

Procedure	All	Treatment group			Control-treatment group		
	Visit 1	Visit 2A	Visit 3A	Visit 4A	Visit 2B	Visit 3B	Visit 4B
Informed consent	x						
Participant demographics	x						
Medical history and medications	x						
Contact lens history	x						
Comfortable & total contact lens wear time	x		x	x	x	x	x
CLDEQ-8, SPEED questionnaire, OSDI questionnaire	x		x	x	x	x	x
Visual acuity	x		x	x	x	x	
Non-invasive tear break-up time	x						
Lipid layer assessment	x						
Meibomian gland secretion assessment	x		x	x	x	x	
Meibomian gland imaging	x						
Slit lamp biomicroscopy	x		x	x	x	x	
Contact lens assessment	x						
Pre-lens tear break-up time	x		x	x	x	x	
Lid margin cleaning		x			x		
iLux® treatment		x			x		
Blink exercises - teach & practice		x			x		
Study exit				x			x

4.5.1 DEMOGRAPHICS

Demographic information from participants will be obtained, including age, sex, medical conditions, medications, allergies, management of dry eye symptoms. Medical history questions to determine any medical conditions, prior/concomitant medications and any allergies will be asked and documented.

4.5.2 CONTACT LENS HISTORY

Information will be obtained from the participant about the current contact lens type (lens name, brand), lens power, contact lens care solution, number of lens wear days, lens wear time (total and comfortable) and use of rewetting drops.

4.5.3 QUESTIONNAIRES

4.5.3.1 CLDEQ-8

The Contact Lens Dry Eye Questionnaire (CLDEQ-8) is a validated questionnaire recommended by the 2013 TFOS Workshop on Contact Lens Discomfort as the best approach for detecting contact lens discomfort (CLD).⁵ A cut-off score ≥ 12 suggests CLD is present and the CL wearer would benefit from clinical management of the CL-related symptoms.⁶

4.5.3.2 SPEED

The Standard Patient Evaluation of Eye Dryness (SPEED) questionnaire (TearScience, Morrisville, NC) is a dry eye questionnaire developed to assess the frequency (0-3 scale) and severity (0-4 scale) of patient symptoms and reviews the presence of symptoms within the past 72 hours and past 3 months.⁷ Scores range from 0-28, with higher values indicating more severe dryness.

4.5.3.3 OSDI

The Ocular Surface Disease Index (OSDI) questionnaire (Allergan, Irvine, CA) is a dry eye questionnaire that asks the participant to reflect and rate over the past week, their symptoms of eye dryness in different working conditions and environments. A higher composite score indicates more severe dryness.⁸

4.5.4 VISUAL ACUITY

Visual acuity will be measured using high contrast computer-generated acuity charts. Participants will be asked to read letters that progressively decrease in size on a computer screen located at a distance of 6 meters.

4.5.5 NON-INVASIVE TEAR BREAK-UP TIME AND PRE-LENS TEAR BREAK-UP TIME

The participant will be seated in front of a device that will project rings of light (Placido discs) onto the tear film. The participant will be asked to keep their eyes open for as long as they can and the time until the rings first begin to distort or break will be recorded. Three measurements will be taken to obtain an average value.

4.5.6 LIPID LAYER ASSESSMENT (LIPIVIEW II)

The participant will be seated at the LipiView II instrument which will image and compute the lipid layer thickness of the tear film. Prior to the commencement of this test, no history of seizures or discomfort with rapidly blinking lights will be reconfirmed.

4.5.7 MEIBOMIAN GLAND SECRETION ASSESSMENT

Meibomian gland dysfunction results in stagnation of the meibum (oil) within the glands. The ease of expression of the gland and the quality of the expressed contents therefore provides an indication of the functional capabilities of the glands. The MG Evaluator (TearScience/J&J) will be used to apply a pressure of 1.2g/mm² to the lower eyelid just inferior to the lid margin in three areas – nasal, central and temporal. Five consecutive glands in each area will be assessed for expressibility. Glands will be graded as follows: 0: No secretion (includes capped orifices), 1: inspissated (toothpaste), 2: colored/cloudy with debris, 3: clear liquid oil. The results for each location will be summed (Meibomian gland secretion score, MGS, range = 0 to 45). A score of ≤ 15 (on a scale of 0 to 45) for 15 glands of the lower lid in both eyes is required to be eligible for this study. In addition, the total number of functional Meibomian glands, defined as having a liquid section with a grade 2 or 3, will be counted (range = 0 to 15).

4.5.8 MEIBOMIAN GLAND IMAGING

While seated at the OCULUS Keratograph 5M, the participant will be asked to place their chin on the chin rest and head against the forehead rest. The lower lid will be everted and infrared images will be taken of the exposed palpebral surface. This will be repeated for the upper eyelid.

The grading of Meibomian gland dropout will be conducted on the images after all participants are completed. Images will be graded according to Pult's 5-grade meiboscale (Figure 3).⁹

[figure not shown]

Figure 3: Meiboscale for grading the percentage of Meibomian gland dropout⁹

4.5.9 SLIT LAMP BIOMICROSCOPY

A slit lamp biomicroscopy examination will be conducted to assess anterior segment ocular health. The participant will be seated behind a slit lamp and the ocular findings will be graded using the Efron grading scale (0-4, 0.1 steps – unless otherwise stated):

External adnexa anomalies

The presence or absence of external adnexa anomalies will be recorded. If detected, the anomaly will be described.

Lids

The presence or absence of the following findings will be recorded:

- Erythematous lid margins
- Thickened lid margins
- Significant telangiectasia
- Irregular or serrated lid margins
- Blepharitis
- Other lid conditions: entropion, ectropion, significant lid oedema, trichiasis, ptosis, lagophthalmos, blepharospasm

Bulbar and limbal hyperemia

The redness of the bulbar and limbal conjunctiva of both eyes will be assessed.

Cornea

The presence or absence of scars or other corneal observations will be recorded and described.

Endothelium abnormalities:

The presence or absence of endothelium abnormalities will be recorded and described.

Anterior chamber

The presence or absence of anterior chamber reaction will be recorded and described.

Other abnormalities

The presence or absence of other abnormalities will be recorded and described.

Corneal and conjunctival staining

A sodium fluorescein strip, wetted with a few drops of saline, will be applied to the inferior temporal tarsal conjunctiva of both eyes. Staining will be graded while viewing with cobalt blue light through a Wratten no. 12 barrier filter.

Palpebral conjunctival hyperemia and papillae (roughness)

The redness and roughness of the upper and lower eyelids will be assessed.

4.5.10 CONTACT LENS FIT ASSESSMENT

Contact lens fit:

Lens fit will be assessed to ensure acceptable lens fit with the participant's habitual contact lenses.

The following will be assessed:

- Monocular & binocular distance logMAR visual acuity (high contrast, high illumination)
- Centration in primary gaze (scale: optimal, slight decentration, moderate decentration but not encroaching limbus, excessive & occasionally encroaching limbus)
- Post-blink movement in primary gaze (mm)
- Lens tightness (push-up test) in primary gaze (0-100, where 0= falls from the cornea without lid support, 50 = optimum, 100 = no movement)
- Overall fit (0-4, where 0=lens should not be worn at all, 4= perfect)

Contact lens wettability and deposits:

Contact lens wettability and deposits will be graded with participant's habitual and study lenses using 32x magnification, on a 0-4 scale in 0.25 steps where 0 = excellent wettability, 0= no deposits.

4.5.11 LID MARGIN CLEANING

The lower lid margins of both eyes, including the area directly over the Meibomian gland orifices, will be cleaned prior to administering iLux® treatment. Cleaning the lid margins will remove any devitalized cellular material and other accumulated buildup along the lid margins.^{10, 11} A golf club spud is used to gently remove debris, with anesthetic. This procedure is not intended to remove tissue that cannot be removed with gentle motion and gentle pressure of the golf club spud. The participant should not experience discomfort. The "wet" conjunctiva will not be debrided. The following steps will be taken:

1. Instill one drop of Alcaine (0.5% proparacaine hydrochloride). Soak a cotton tip with Alcaine and dab the cotton tip along the lid margins.
2. A sodium fluorescein strip, wetted with a few drops of saline, will be applied to the inferior temporal bulbar conjunctiva of both eyes to aid visualization of the Line of Marx.
3. With the participant seated at the slit lamp (16x magnification), the participant will be instructed to look up.
4. The golf club spud will be placed onto the lid margin, directly over the Line of Marx which should be stained with fluorescein.
5. The golf club spud will be gently maneuvered in small wiping motions (nasal to temporal or vice versa) with mild pressure across the entire length of the Line of Marx.
6. After cleaning the Line of Marx, examine the lid margin to ensure there are no stained cells visible.
7. After cleaning the Line of Marx, any remaining accumulated debris on the keratinized lid margin and any accumulated material potentially obstructing the Meibomian gland orifices will be removed. The golf club spud will be placed onto the keratinized lid margin with **the tip of the spud placed at the edge of the Line of Marx** which was previously cleaned.
8. The golf club spud will be gently maneuvered in small wiping motions (nasal to temporal or vice versa) with mild pressure across the entire length of the keratinized lid margin surface, covering all areas **from the edge of the Line of Marx to the base of the lashes at the lash line.**

9. After cleaning the keratinized lid margin, examine the lid to ensure that little to no sheen is visible on the lid margin surface, and any functional Meibomian gland orifices are exposed.
10. For the upper lid, the participant will be instructed to look downwards during the procedure.
11. The participant is instructed to notify the investigator if they experience any discomfort during any part of this procedure.

4.5.12 ILUX® TREATMENT

The upper and lower eyelids of both eyes will be treated with the iLux device using a single disposable Smart Tip. Each eyelid will be divided into two treatment zones: nasal-central, central-temporal. Each zone will be treated for all eyelids of both eyes. The same procedure is applied for each zone. A new Smart Tip will be used for each new participant. One drop of Alcaine (0.5% proparacaine hydrochloride) will be instilled to each eye immediately before iLux® treatment.

The following steps will be taken:

1. With the participant reclined, instruct the participant to look up (if treating the lower lids) or down (if treating the upper lids).
2. Slide the inner pad behind the eyelid positioned to the treatment zone. Confirm the appropriate position by looking through the magnification panel of the device.
3. Slide the Heater Control Switch forward to slide the outer pad gently hold the eyelid in position and deliver heat to the treatment zone.
4. Deliver heat to the treatment zone for 40-90 seconds (indicated by the “melting time” value on the screen display) while looking through the magnifying lens. The duration of heat application is dependent on the quantity of meibum expressed from the glands in the treatment zone.
5. After the application of heat, slide the Heater Control Switch to deactivate the heating LED lights and to move the device to the expression phase.
6. Perform 4 rounds of compression, lasting 5 seconds each. Keep visualizing the quantity and quality of meibum expressed from the glands.
7. Gently remove the inner pad from the eyelid and repeat the process on the remaining treatment zones for each eyelid.
8. Participants will be instructed that they can resume contact lens wear one hour after completion of iLux® treatment unless there is an adverse event, as determined by the investigator and participant. In the case of an adverse event (e.g. ocular surface irritation,

inflammation or discomfort), participants will be advised when to resume contact lens wear following resolution of the event.

4.5.13 BLINKING EXERCISES

After the administration of the iLux® treatment, the participant will be instructed on how to perform blinking exercises. These exercises will be performed daily, every hour for a minimum 10 times per day until the 1 month follow-up visit to ensure the flow of oils from the Meibomian glands is sustained. The exercises will be practiced with the participant before they leave after their treatment, and will also receive the information on a printed handout. Participants will be instructed to:

1. Place their fingers at the corner of their eyes to feel the lid movement.
2. Close their eyelids together with the upper and lower lids completely touching for a count of 2. When the lids are closed correctly, the participant should not feel like movement under their fingers.
3. Squeeze their eyelids lightly for a count of 2. When squeezing their eyelids lightly, they should feel slight lid movement under their fingers. With a moderate squeeze, they should feel the contraction of the lid muscles under their fingers.
4. Open their eyelids for a count of 2.
5. Repeat the cycle nine more times to reach a total of 10 repetitions: CLOSE and count 1 and 2 - SQUEEZE and count 1 and 2 - OPEN and count 1 and 2.

5 MONITORING PROTOCOL ADHERENCE

All study personnel, including investigators, will undergo training on the protocol and their specific role. Procedures for monitoring and reporting protocol deviations are described in the protocol (Section 13.4).

6 POTENTIAL RISKS AND BENEFITS TO HUMAN PARTICIPANTS

This is a minimal risk study because of the use of marketed device and standard optometric assessments.

Contact lenses in this study will be worn on a daily wear basis, for at least 5 days per week and at least 6 hours per day. Adverse events and/ or complications in daily wear of soft contact lenses can occur (e.g. inflammation and infection). When contact lenses are worn on a daily wear basis, there is a small risk of an adverse event compared to not wearing contact lenses. When contact lenses are worn on an extended wear basis, there is a significantly increased risk of an adverse reaction compared with wearing contact lenses on a daily wear basis. As participants will be

wearing their habitual contact lens type in this study, there is no increased risk from wearing the lenses in this study. Due to the daily wear nature of the study, this study considered a non-significant risk study based on United States Food and Drug administration (FDA) and International Standards Organization (ISO) guidelines.

This study will provide participants with one treatment with the iLux® device. A safety study has found that iLux® treatment does not cause excessive heating of the cornea, outer eyelid or surrounding surface. It is possible that participants may experience: eyelid/eye pain requiring discontinuation of the treatment procedure, eyelid irritation or inflammation, temporary reddening of the skin, ocular surface irritation or inflammation (e.g., corneal abrasion, conjunctive oedema or conjunctival hyperemia), and ocular symptoms (e.g., burning, stinging, tearing, itching, discharge, redness, foreign body sensation, visual disturbance, sensitivity to light).

Additionally, it is possible that participants may experience temporary discomfort associated with the other study procedures including: burning and stinging, blurred vision, sandiness or grittiness, light sensitivity, dryness, itching, crusty eyes and foreign body sensation. The use of topical numbing (anaesthetic) eye drops may also cause stinging, burning or an allergic reaction. A dye (fluorescein) normally used for eye exams is being used in this study. Although rare, it is possible that participants may have any allergic reaction to the dye. This could cause discomfort to their eye.

Participants may benefit directly from taking part in this study as they will receive a treatment that will manage their dry eye disease that may improve their contact lens wear experience. Information from this study may help researchers come up with new management options to help others with contact lens discomfort in the future. Participation in this study may contribute to scientific research information that may be used in the development of new treatments for dry eye disease and contact lens discomfort.

7 ADVERSE EVENTS

See CORE SOP012_v02 for a description of all adverse events, including management and reporting.

An 'adverse event' (AE) refers to any untoward medical occurrence in a subject administered an investigational product or subjected to an investigational study procedure. Any observations taking place prior to determining that a subject meets all inclusion / exclusion criteria for the study and which are not related to the performed study procedures are not considered an AE. An AE can

therefore be any unfavorable and unintended sign, symptom, or disease temporarily associated with the investigational product / study procedure, whether there is a causal relationship or not.

8 DISCONTINUATION FROM THE STUDY

Participants may be discontinued at the discretion of the investigator or sponsor in consideration of participant safety or protocol compliance, or at discretion of the participant. Participants discontinued from a study will be reimbursed \$20 per hour for their active involvement in the study (including the initial screening visit). Data will not be included in statistical analysis, unless permission is granted by the participant at the time of discontinuation. The following is a list of possible reasons for discontinuation from the study:

- Screening failure: Participants will be discontinued if they do not meet the inclusion and exclusion criteria outlined in section 4.2.3.
- Unacceptable performance with products to be used in study: Participants may be discontinued if they are unable to achieve acceptable comfort and /or vision with the study products.
- Positive slit lamp finding: Participants may be permanently discontinued from the study depending on the severity of the condition and on the judgement of the investigator.
- Adverse event: If a participant experiences an adverse event during the study they may be discontinued based on the clinical judgement of the investigator.
- Symptoms: If the participant has persistent symptoms they may be discontinued based on the clinical judgement of the investigator.
- Disinterest, relocation or illness: The participant may choose to discontinue due to reasons within or beyond their control.
- Violation of protocol or non-compliance: The participant will be discontinued if they are unable or unwilling to follow the protocol specified visit schedules and/or study procedures.
- Instillation of topical ocular medication: The participant will be discontinued if they elect to use a topical ocular medication during the study unless that topical ocular medication is prescribed for a limited duration (less than two weeks) to treat a transient condition; in this case the participant may remain an active participant (at the discretion of the

investigator) after stopping topical ocular medication following resolution of the ocular condition).

- Lost to follow-up: The participant will be discontinued if they cannot be contacted and do not return for a final exit visit, and if the investigator has made a reasonable effort to contact the participant for a final study visit.
- Premature termination of the study by the sponsor, CORE or the Office of Research Ethics at the University of Waterloo.

A discontinuation form stating the reason for discontinuation will be completed, which requires the signatures of both the participant and the investigator except where the participant is lost to follow-up in which case only the signature of the investigator is required.

All discontinuations including their reasons will be included in the final report.

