4.2.2 NUMBER OF PARTICIPANTS

Participants will be recruited using CORE records and advertising approved by the University of Waterloo Office of Research Ethics. Participants expressing an interest in the study will be pre-screened using the CLDEQ-8 questionnaire to assess whether they meet the symptomatic contact lens wear criteria. However, eligibility for the study can only be determined at the screening visit using the inclusion and exclusion criteria. Data from the pre-screening questionnaire will not be considered as study data and will be confidentially disposed of. This questionnaire will be repeated at the screening visit and stored as study data.

Up to 52 eligible participants will be randomized with a target of 46 participants completing the study. Informed consent will be obtained for all participants prior to their enrolment in the study.

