4.4 SCHEDULED AND UNSCHEDULED VISITS

4.4.1 STUDY VISITS

This study has a total of 4 study visits, including the screening visit. The total time commitment for this study for the treatment group is 3.5 hours. The total time commitment for the control-treatment group is 4.0 hours. Participants randomized to the treatment group will be involved in the study for three months. Participants randomized to the control-treatment group will be involved in the study for four months. Table 4 summarizes the study visits.

Table 4: Summary of visit codes

Visit #	Day/s	Visits	Duration (hours)
For all participants			
Visit 1	0	Screening	1.0
For participants randomized to the treatment group			
Visit 2A	0	iLux® treatment	0.5
Visit 3A	23 - 37 days after Visit 1	1 month follow-up	1.0
Visit 4A	83 - 97 days after Visit 1	3 month follow-up & study exit	1.0
For participants randomized to the control-treatment group			
Visit 2B	23 - 37 days after Visit 1	Assessment & iLux® treatment	1.5
Visit 3B	23 - 37 days after Visit 2	1 month follow-up	1.0
Visit 4B	83 - 97 days after Visit 2	3 month follow-up & study exit	0.5

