4.4.3 TREATMENT GROUP

4.4.3.1 ILUX® TREATMENT (VISIT 2A)

Visit 2 occurs immediately after Visit 1 for participants that have been randomized to the treatment group. The following procedures will be conducted:

1. The participant will remove their contact lenses.
2. The participant's eyelids will be cleaned by the investigator.
3. The iLux® treatment will be administered to both eyes by the investigator.
4. A slit lamp biomicroscope examination will be performed as a safety check.
5. The participant will be provided with verbal and written instructions on how to complete blinking exercises. One round of blinking exercises will be completed with the investigator to ensure the participant understands the instructions.
6. Monocular & binocular distance logMAR visual acuity (high contrast, high illumination) with habitual spectacles as a safety check.

4.4.3.2 1 MONTH FOLLOW-UP (VISIT 3A)

Participants will attend this visit 23-37 days after iLux® treatment administered at Visit 2. Participants will attend this visit wearing a new pair of their habitual CLs for ≥ 4 hours prior to the visit. Participants who attend not meeting this criteria will be rescheduled (unless they report problems when wearing their lenses). The following procedures will be conducted:

1. Review medical history (changes in medication, adverse events)
2. Collect information on participant's CL wear habits:
 - a. Average total wear time (number of days per week, number of hours per day)

- b. Average comfortable wear time (number of hours per day).
3. The participant will complete the CLDEQ-8 questionnaire, SPEED questionnaire and OSDI questionnaire.
4. Monocular & binocular distance logMAR visual acuity (high contrast, high illumination) with habitual CLs.
5. Assess pre-lens tear film break-up time.
6. The participant will remove their CLs.
7. Meibomian gland secretion assessment using the Meibomian gland evaluator.
8. Ocular health assessment including ocular surface staining.
9. The participant will be allowed to reapply their habitual CLs or wear their own spectacles. Monocular & binocular distance logMAR visual acuity (high contrast, high illumination) with visual correction.

4.4.3.3 3 MONTH FOLLOW-UP VISIT AND STUDY EXIT (VISIT 4A)

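### Section 8 drops a discontinued participant's data by default, including a 1-month SPEED score already collected, and participants lost to follow-up cannot give the permission that would keep it

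*Combined protocol and SAP*

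**What the plan says.** Section 8 sets the rule for participants who leave early: "Data will not be included in statistical analysis, unless permission is granted by the participant at the time of discontinuation". Exclusion is the default, and the sentence does not separate data recorded before discontinuation from anything later.

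The same section counts loss to follow-up as a discontinuation: "The participant will be discontinued if they cannot be contacted and do not return for a final exit visit". A discontinuation form is signed by participant and investigator, "except where the participant is lost to follow-up in which case only the signature of the investigator is required".

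Some other listed reasons can be related to symptoms. One is discretionary: "If the participant has persistent symptoms they may be discontinued based on the clinical judgement of the investigator". Another is mandatory: "The participant will be discontinued if they elect to use a topical ocular medication during the study unless that topical ocular medication is prescribed", the exception being a course of under two weeks for a transient condition.

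The primary endpoint is the change in SPEED at 1 month (section 2). At Visit 3A for the treated (section 4.4.3.2) and Visit 2B for controls (section 4.4.4.1), "The participant will complete the CLDEQ-8 questionnaire, SPEED questionnaire and OSDI questionnaire". Both arms then continue: the treated to about 3 months, while "Participants randomized to the control-treatment group will be involved in the study for four months" (section 4.4.1). Section 4.2.2 plans the losses: "Up to 52 eligible participants will be randomized with a target of 46 participants completing the study". Section 10.1 names the tests but gives no analysis set or missing-data method that would bring excluded scores back.

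**The concern.** A primary-endpoint score that has been validly collected should be analysed in the group to which the participant was randomised, unless the participant withdraws consent for its use. Here a score can be removed because of something that happens weeks later, without the participant having objected.

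This matters more than usual for three reasons. The trial is unmasked (section 4.1.3) and the endpoint is a symptom score, so the decision to leave can depend on both outcome and arm. The period at risk after the primary score differs by arm, and controls have their treatment session within it. And for anyone lost to follow-up the permission route is closed by definition. Section 8 does require discontinuations and their reasons to be reported; that discloses the loss but does not restore the scores.

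**Working it through.** **1. The plan's own sample size.** Inputs from section 4.2.1: effect size d = 1.0, 90% power, two-sided alpha 0.05, 10% dropout. The noncentral-t calculation gives 22.02, rounded up to 23 per group. 23 / 0.9 = 25.6, so 26 per group and 52 in total. The plan's figures reproduce.

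**2. Time at risk after the primary score.** Midpoints of the windows in Table 4 (section 4.4.1):
- Treated: 1-month score at day 30, exit at day 90, leaving 90 − 30 = 60 days.
- Control: 1-month score at day 30, exit 90 days after Visit 2, so day 120, leaving 120 − 30 = 90 days.

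**3. How many leavers would already hold a score.** Planned losses are 52 − 46 = 6. Assume a constant daily dropout rate h, equal in both arms (not in the documents):
- 26 × (2 − e^(−90h) − e^(−120h)) = 6 gives h = 0.00117 per day.
- Lost before day 30: 26 × (1 − e^(−30h)) = 0.9 per arm.
- Lost after day 30: treated 26 × (e^(−30h) − e^(−90h)) = 1.7; control 26 × (e^(−30h) − e^(−120h)) = 2.5.
- Total 4.2 of 6, or 3.7 to 4.7 across the visit windows.

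This counts leavers who hold a score. It equals the number of scores lost only if none of them gives permission, so it is an upper bound for this dropout model.

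**4. Loss unrelated to outcome.** About 25 per arm reach the 1-month score (26 − 0.9 = 25.1). Noncentral-t power at d = 1.0 is 93.4% with 25 per arm and 91.2% with 23 per arm. The cost is about 2 percentage points, and power stays above the 90% target.

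**5. Loss related to outcome in one arm.** Simulation of normal scores with no true effect, 25 per arm and a two-sided 5% t-test. Treated leavers are chosen by a variable correlated r = 0.5 with their 1-month score (assumed), worse scores leaving; the same number of controls leave at random.

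| Lost per arm | Shift favouring treatment | False-positive rate |
|---|---|---|
| 1 | 0.04 SD | 5.3% to 5.4% |
| 2 | 0.08 SD | 5.9% to 6.0% |

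The ranges are the spread over repeated runs. As a check on the shift, it should equal r × m × k / (25 − k), where m is the expected mean of the k largest of 25 standard normal values (1.97 for k = 1, 1.74 for k = 2): 0.5 × 1.97 × 1/24 = 0.041 and 0.5 × 1.74 × 2/23 = 0.076.

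In SPEED points, section 4.2.1 cites an 8-point improvement as an effect size of 1.8, in a study of another device. That implies an SD of 8 / 1.8 = 4.4, so the larger shift is 0.076 × 4.4 = 0.3 points on a 0 to 28 scale.

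**The case against.** The strongest reply is that the rule will rarely bite. Apart from loss to follow-up, every leaver signs the discontinuation form, which gives an occasion to ask, and many may agree. If half of the roughly 4 scores were kept (an assumption), about 2 would be lost, or 1 per arm: the first row of the table. Random loss is already budgeted for. Discontinuation for symptoms is discretionary, everyone enters with symptoms, and nothing in the protocol makes lack of improvement a reason to stop. Data use after withdrawal is also partly a consent matter, and the consent letter was not available to check.

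Most of this stands, and it limits the size of the point. It does not remove it: section 8 still excludes by default, the form is described only as recording a reason and signatures, and those lost to follow-up cannot be asked.

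A reader might infer more than the documents support:
- **That about 4 primary scores will be lost.** The documents give neither the timing of dropout nor the share who would refuse permission.
- **That the rule favours the device.** Treated non-responders drifting away would have that effect, but this is conjecture. Selective loss of symptomatic controls would work the other way and cost power.
- **That false positives could reach 13%.** That needs the three worst scorers removed from the treated arm, none from the control arm, and no permission given. It is a ceiling and should not drive the rating.

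**Conclusion.** The point holds as a defect in a stated rule. Section 8 can discard primary-endpoint scores already collected in an unmasked trial, does so automatically for participants lost to follow-up, and is not overridden by section 10.1.

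The likely effect is small: at most about 4 scores under a constant dropout rate, no breach of planned power if loss is random, and a 0.04 to 0.08 SD shift with 5.3% to 6% false positives in the illustrative selective cases. Those cases rest on the assumed correlation of 0.5, on selection in the treated arm only, and on 1 or 2 scores lost per arm. Actual direction and size cannot be known from the documents. The change is worth making because the loss is avoidable at almost no cost, not because the result is likely to be overturned.

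**What to change.** Replace the sentence in section 8 with: *For randomised participants, all data collected up to discontinuation will be analysed in the randomised group unless the participant withdraws consent for their use.* Align the consent letter and the discontinuation form. The limit to randomised participants is needed because section 8 also lists screening failures as discontinuations. The right to withdraw data is kept, and the investigator's discretion to discontinue is unchanged.

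Optionally, ask participants discontinued before their 1-month assessment, who have not withdrawn consent, to complete the 1-month questionnaires. A 3-month assessment of untreated controls is not needed, because no comparison in section 10.1 would use it.

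Cost: amended wording in three documents. Scores already collected cost nothing more to obtain. The optional questionnaires would involve about 2 people (0.9 per arm in step 3); at half an hour each (the length of Visit 4B) and $20 per hour, 2 × 0.5 × $20 = $20, plus staff time. The downside is that some retained participants may have used other treatment before their 1-month score, which must be recorded and reported.
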